j Blood samples for antipsychotic plasma concentrations will be collected at Screening, Day -2, Day 1 (approximately 10 minutes prior to dosing), Day 2 (2 - 4 hours postdose), Day 7 (2 – 4 hours postdose), Day 14 (prior to PET scan), and at Follow-up.

k Additional urine drug screen may be ordered as deemed clinically appropriate. These results should be discussed with the Medical Monitor.

l Each PET scan will be accompanied by intravenous administration of radiotracer  $^{18}\text{F}$ -DOPA and oral pre-treatment (1 hour prior to tracer) with 150 mg carbidopa and 400 mg entacapone. If PET/MR scanner is unavailable for technical reasons separate PET and MR scans (on an alternate PET scanner without MR and alternate MR scanner) will be permitted. Prior to each PET scan, there is a period of resting state fMRI collection. In addition to fMRI scan sequences, exploratory MRI sequences may be performed during each of the MRI and PET/MR acquisition times and may include (but not limited to) a neuromelanin-sensitive MRI (NM-MRI) sequence and an iron-sensitive MRI sequence (effective transverse relaxation rate [R2\*] or Quantitative Susceptibility Mapping [QSM]). Repeat MRI including exploratory MRI sequences may be performed where it is not possible to obtain complete measures during the PET-MRI scan.

m In the event of unsuccessful PET scan on Day 14, additional days of dosing may be necessary up to, but not exceeding, Day 19. If any such additional days are necessary, subjects will continue their usual daily dosing. PANSS, BNSS, MADRS, and CGI-S may be assessed  $\pm 1$  day of PET scan; other assessments are to be completed the same day as the PET scan. Participants will only receive 3 PET scans in the event that a scan is not able to be completed or is not suitable for analysis. It is expected that the majority of participants will receive up to 2 PET scans which would result in an effective dose of 7.4 mSv.

n PET scan to be performed at early termination (ET) visit only if the subject terminates the study prior to Day 14 PET scan.

o Only perform PANSS, BNSS, CGI-S, and MADRS if subject discontinues prior to Day 14 scan day.

p At the screening visit, the “Baseline/Screening” version will be completed; the “Since Last Visit” version of the C-SSRS will be administered for all other visits. C-SSRS should be performed prior to PET scan on Day 14.

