### 7.3.2. Rationale for the Dosages

Study SEP361-118 will employ a flexible dosing regimen. After initiation at a SEP-363856 dose of 50 mg/day for 3 days, subjects are required to titrate up to 75 mg/day. Subjects may reduce the dose once to 50 mg/day for tolerability reasons at any time. Subjects who have a dose reduction for tolerability will continue to receive the reduced dose for the remainder of the study. This dosing scheme is nearly identical to the dosing regimen utilized in the current, clinically complete Phase 2 study in patients with schizophrenia (Study SEP361-201).

SEP-363856 50 mg/day and 75 mg/day were selected based on the safety and tolerability observed profiles for single and multiple oral doses of SEP-363856 given to healthy adult male subjects and adult subjects with schizophrenia during the clinical development program. Results of completed studies demonstrated that the maximum tolerated single SEP-363856 dose was 50 mg for healthy adult volunteer subjects and 100 mg for adults with schizophrenia. Single doses of SEP-363856 were also shown to have robust central nervous system (CNS) activity in completed fMRI study (SEP361-104). Dose selection is further supported by safety and tolerability results after dosing with SEP-363856 10 mg - 100 mg/day for 7 days and dosing with SEP-363856 75 mg/day for 28 days in adults with schizophrenia (Study SEP361-106, Parts 1 and 2).

The PET ligand F-DOPA will be used at each of the PET scans in this study. Up to 150 MBq of F-DOPA will be intravenously administered at the start of each PET scan. The total radiation exposure from each PET scan is up to 3 mSv, and each PET scan will be accompanied by up to 2 low dose CT scans resulting in up to 0.7 mSv. The total effective dose from this study is therefore up to  $3 * (3.0 + 0.7) = 11.1$  mSv, placing it in the III category of the International Commission on Radiological Protection (ICRP) classification, suitable for research studies in human subjects. The effective dose of 11.1 mSv is equivalent to 4.8 years of naturally occurring background radiation. For an adult in good health, this is calculated to result in a risk of approximately 1 in 1800 in induction of fatal cancer. This dose has been selected as it provides images of suitable quality while minimizing the radiation exposure to participants. The majority of participants will receive up to 2 PET scans, which would result in an effective dose of

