7.4 mSv. Participants will only receive 3 PET scans in the event that a scan is not able to be completed or is not suitable for analysis.

One hour prior to each PET scan, single doses of 150 mg carbidopa and 400 mg entacapone will be given orally to reduce the peripheral metabolism of F-DOPA, and the formation F-DOPA metabolites, thereby improving the quality of the acquired brain images. Both drugs are approved at the doses administered for human use and will be administered approximately one hour before the scan. No drug interaction concerns are anticipated with the limited exposure to carbidopa and entacapone.

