#### **7.4. Prevention of Missing Data**

In an effort to minimize the number of subjects who withdraw consent prior to study completion, the number of visits and assessments has been limited to those required to collect the information needed to address the objectives of the study. The number of PET scans and collection of blood samples are essential components of the study, therefore, subjects will remain in the overnight confinement unit until the completion of the postdose PET scans and blood sample collection (all assessments will be performed in the clinic).

Day pass may be granted during the study due to emergency unavoidable personal reasons with prior approval from the Medical Monitor. The pass must be of limited duration. The subject must be considered by the Investigator to be clinically stable and Investigators should follow standard facility or institutional procedures to ensure subject safety during the pass. The reason for and duration of the day pass as well as Medical Monitor approval must be documented. Subjects will receive an unscheduled urine drug screen upon return to site.

A concerted effort by the clinical team will be made to enroll subjects with good venous access. In addition, every effort will be made to have subjects return for the end of study visit to collect follow-up safety data. In the case of failure to obtain adequate data from a measure (eg due to scan failure due to technical reasons), the measure may be repeated if feasible (total radiation dose to remain within guidelines for exposure for research purposes).

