## **8.2. Subject Exclusion Criteria**

To qualify for participation, subjects must not meet any of the following exclusion criteria at Screening and Day 1 (including all available predose assessments):

1. Subject answers “yes” to “Suicidal Ideation” Items 4 (active suicidal ideation with some intent to act, without specific plan) or Item 5 (active suicidal ideation with specific plan and intent) on the C-SSRS at or during the Screening period (ie, in the past one month) and/or Day 1 (ie, since last visit).
2. Subject does not tolerate venipuncture or has poor venous access that would cause difficulty for administration of the radioisotope and for collecting blood samples.
3. Subject is currently participating in, or has participated in, a study with an investigational or marketed compound or device within 3 months prior to signing the informed consent, or has participated in more than 2 studies of investigational compounds within 24 months prior to signing the informed consent.
4. Subject has participated in a research and/or PET or radiological investigations with radiation exposure that, when combined with the dose from the present study, would exceed 10 mSv in addition to natural background radiation, in the previous 12 months.
5. Subject has previously received SEP-363856.

6. Subject has any clinically significant unstable medical condition or any clinically significant chronic disease that in the opinion of the Investigator, would limit the subject's ability to complete and/or participate in the study:
  - a. Clinically significant hematological (including deep vein thrombosis) or bleeding disorder, renal, metabolic, endocrine, pulmonary, gastrointestinal, urological, cardiovascular, hepatic, neurologic, or allergic disease (except for untreated, asymptomatic, seasonal allergies at time of dosing).
  - b. Subject has a history of malignancy within 5 years prior to the Screening visit, except for adequately treated basal cell or squamous cell skin cancer or in situ cervical cancer. Subject has a pituitary tumor of any duration.
  - c. Disorder or history of a condition, or previous gastrointestinal surgery (eg, cholecystectomy, vagotomy, bowel resection) that may interfere with drug absorption, distribution, metabolism, excretion, gastrointestinal motility, or pH, or a history of clinically significant abnormality of the hepatic or renal system, or a history of malabsorption.

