### 11.4. PET/fMRI Assessments

It is important that the participant is examined under the same conditions at baseline and subsequent scan, including scanning at the same time of day where possible (scanning time of day should be  $\pm$  3h from the time of day of the baseline scan where possible), and head motion monitored and minimised. The post-dose scan should be timed to occur so that the start is approximately at the time in which maximum observed plasma concentration ( $C_{max}$ ) occurs. Post dose fMRI scanning will start approximately 2 to 4 hours after dosing.

Prior to entry into the scanner, subjects will complete the site's standard radiography screening questionnaire to ensure they are safe to enter the scanner environment (eg, no history of surgery involving metal implants). Females will undergo urine pregnancy test to exclude pregnancy. Scan date as well as start and stop time will be collected.

Approximately 1 hour before the scan participants will receive 150 mg of carbidopa and 400 mg of entacapone orally. This inhibits the formation of radiolabeled metabolites of F-DOPA that may cross the blood-brain barrier, and boosts the signal to noise ratio. Subjects will have an IV canula placed in the ante-cubital fossa for administration of F-DOPA. Prior to scanning they will be asked to go to the toilet.

Striatal dopamine synthesis capacity (DSC) assessment ( $K_i$ ) using  $^{18}\text{F}$ -DOPA kinetic analysis will be performed.

In addition to fMRI scan sequences, exploratory MRI sequences may be performed during each of the MRI and PET/MR acquisition times and may include (but not limited to) a neuromelanin-sensitive MRI (NM-MRI) sequence and an iron-sensitive MRI sequence (effective transverse relaxation rate [ $R_2^*$ ] or Quantitative Susceptibility Mapping [QSM]). Repeat MRI including exploratory MRI sequences may be performed where it is not possible to obtain complete measures during the PET-MRI scan.

The majority of participants will receive up to 2 PET scans. Participants will only receive 3 PET scans in the event that a scan is not able to be completed or is not suitable for analysis.

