## **11.9. Study Visits and Assessments**

See [Table 2](#) Schedule of Assessments, for a summary of procedures at each study visit.

### 11.9.1. Screening (Day -49 to Day -2): Visit 1

A unique screening number will be assigned to each subject.

Subjects will be evaluated at the Screening Visit to determine their eligibility to enroll in the study. No imaging procedures involving ionizing radiation will be performed within 12 hours of written consent.

Procedures may be completed in any order unless specified otherwise.

The following study-related procedures will be performed at Screening (procedures will occur over multiple days):

- Obtain signed informed consent and privacy authorization from the subject before conducting any other visit procedures.
- Inclusion and exclusion criteria
- Obtain demographic information.
- Prior/concomitant medications
- Medical history
- Psychiatric history/mental status
- SCID-CT
- Physical examination.
- Height and weight; clinical site staff to calculate and record BMI.
- Vital sign measurements.
- Perform ECG.
- Collect blood sample for clinical laboratory evaluation (hematology, chemistry, serum prolactin, glycosylated hemoglobin [HbA1c], Hepatitis B/C, HIV-1/HIV-2, and fasted glucose panel and lipid panel).
- Collect blood samples for serum pregnancy test (serum human chorionic gonadotropin [ $\beta$ -hCG]) for female subjects and serum follicle stimulating hormone (FSH) for female subjects if menopause is suspected.
- Collect blood sample for antipsychotic levels.
- Collect urine sample for urinalysis and urine drug screen (UDS).
- Perform MRI (MRI at screening must occur prior to the PET scan at screening).
- Perform psychiatric assessments in the following order: PANSS, BNSS, C-SSRS, CGI-S.
- Collect adverse events.
- Perform PET/MR Scan including fMRI (Day -44 to Day -2). Approximately 1 hour before the scan participants will receive 150 mg of carbidopa and 400 mg of entacapone orally.

- Female subjects only, collect urine samples for pregnancy test (any positive test must be followed up with a serum  $\beta$ -hCG test). Urine pregnancy test to be performed on the same day as, but prior to, screening PET/MR Scan.

Subjects who screen fail may be re-screened up to two times, if judged appropriate by the Investigator. Subjects who screen fail due to MRI or PET or fMRI results may not be re-screened.

Re-screened subjects will be re-consented and all screening procedures will be repeated except:

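### Exclusion 4 tests earlier exposure plus an unspecified study dose against 10 mSv although the protocol's own maximum is 11.1 mSv, and re-screening repeats a valid PET that the third-scan rule does not allow

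*Protocol*

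**What the plan says.** **Entry rule.** Protocol Section 8.2, Exclusion 4, applies to subjects who have had "a research and/or PET or radiological investigations with radiation exposure that, when combined with the dose from the present study, would exceed 10 mSv", counted above natural background over the previous 12 months. It gives no figure for the study's own contribution.

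**Study dose.** Section 7.3.2 allows up to 3 mSv per PET scan plus up to 0.7 mSv from accompanying low-dose CT, and multiplies by three scans. It then states: "The effective dose of 11.1 mSv is equivalent to 4.8 years of naturally occurring background radiation". It attaches a fatal-cancer risk of about 1 in 1800 to that total. Table 2, footnote m, gives the usual case: "the majority of participants will receive up to 2 PET scans which would result in an effective dose of 7.4 mSv". Section 7.3.2 repeats the 7.4 mSv figure.

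**Third scan.** Section 7.3.2 says: "Participants will only receive 3 PET scans in the event that a scan is not able to be completed or is not suitable" for analysis. The same rule stands in Table 2 footnote m, Section 10.3.1 and Section 11.4.

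**Re-screening.** Section 11.9.1 permits two re-screens at the Investigator's judgment. It says "Re-screened subjects will be re-consented and all screening procedures will be repeated except" two items: the SCID, which is reviewed and updated, and an MRI from the preceding 90 days. Table 2 footnote a exempts only the MRI. The PET/MR scan is a listed screening procedure and appears in neither list of exceptions. Section 11.9.1 also says: "Subjects who screen fail due to MRI or PET or fMRI results may not be re-screened".

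**General condition.** Section 7.4 lets a measurement that failed to give adequate data be repeated, so long as cumulative radiation stays inside research-exposure guidelines. It gives no number.

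**The concern.** A sum tested against a threshold needs both terms defined. Here one term has two stated values, and they fall on opposite sides of 10 mSv. Two people applying Exclusion 4 to the same subject can reach opposite eligibility decisions, each using a figure printed in the protocol.

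The re-screening text raises a second conflict. Because imaging failures cannot be re-screened, a subject who returns with a screening PET already done did not fail because of that PET. Section 11.9.1 nevertheless has it repeated, while four other places confine a third scan to the case of a failed or unusable one. The text does not say whether the first PET becomes earlier exposure under Exclusion 4.

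At stake is subjects' radiation exposure, for which the protocol states a total and a risk. The primary analysis is not affected.

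**Working it through.** **Inputs (all stated maxima, Section 7.3.2):** PET 3.0 mSv per scan; CT 0.7 mSv per scan. Threshold: 10 mSv (Exclusion 4).

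**Step 1. Reproduce the protocol's figures.**
- Per scan: 3.0 + 0.7 = 3.7 mSv
- Two scans: 2 × 3.7 = 7.4 mSv, as stated
- Three scans: 3 × 3.7 = 11.1 mSv, as stated

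**Step 2. Room left for earlier exposure under Exclusion 4 (10 minus study dose).**

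| Study dose used | Room for earlier exposure | Subject with 1.0 mSv earlier |
|---|---|---|
| 7.4 mSv | 10 − 7.4 = 2.6 mSv | 1.0 + 7.4 = 8.4, eligible |
| 11.1 mSv | 10 − 11.1 = −1.1 mSv, none | 1.0 + 11.1 = 12.1, excluded |

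The two readings disagree for every subject with earlier exposure above 0 and up to 2.6 mSv. Above 2.6 mSv both exclude. A subject with no earlier exposure is not caught by the criterion as worded.

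**Step 3. Consequence of the 7.4 reading if a third scan follows.** The combined exposure is the earlier exposure plus 11.1 mSv: above 11.1 for any earlier exposure, and at most 2.6 + 11.1 = 13.7 mSv. The threshold on which the subject was admitted is then passed by a scan that the protocol permits.

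**Step 4. Re-screening after a valid PET.** The sequence can occur. The PET may be done from Day -44, and eligibility is reviewed again on Day -2, Day -1 and Day 1 (Sections 11.9.2.1 to 11.9.2.3).
- *First PET counted as earlier exposure:* 3.7 + 7.4 = 11.1, above 10. Exclusion 4 bars a re-screen that Section 11.9.1 allows.
- *First PET not counted, one re-screen:* two screening scans plus Day 14 make 3 scans, 11.1 mSv. This equals the stated total, but without the failed scan that the third-scan rule requires.
- *Not counted, two such re-screens:* 4 scans, 4 × 3.7 = 14.8 mSv, which is 14.8 − 11.1 = 3.7 mSv above the stated total.

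Three full screening periods and treatment to Day 19 take 3 × 49 + 19 = 166 days if they run without gaps, so all the scans would fall inside a 12-month window.

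**Step 5. How far this depends on the maxima.** With PET at its full 3.0 mSv, three scans give 9.0 mSv before CT. They stay within 10 mSv only if CT is at most (10 − 9.0) / 3 = 0.33 mSv per scan, against the stated maximum of 0.7.

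**The case against.** The strongest reply is that 7.4 and 11.1 mSv are one per-scan dose multiplied by the usual and the maximum number of scans. Section 7.3.2 presents 11.1 as the study's total, which is the closer match to the wording of Exclusion 4. On that reading the rule is strict but usable, and only a cross-reference is missing. The textual point is fair, but it leaves a criterion written as a 10 mSv sum that allows no earlier exposure at all, and nothing shows that this was intended.

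Second, every dose is an upper limit, so actual sums may be lower. This stands and qualifies all the figures. They are nevertheless the only doses the protocol offers a site for this calculation.

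Third, a third scan is conditional: Section 7.4 ties repeats to exposure guidelines, and Exclusion 4 governs entry, not later dose. This bears on the 13.7 mSv case, since that scan would be a repeat after a failure. But Section 7.4 supplies no number, and it does not reach a re-screen after a valid PET.

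Fourth, a site might follow the specific scan limit over the general instruction to repeat screening, re-screening is discretionary, and a PET from a failed screening fits the words of Exclusion 4. These points make four scans unlikely. They do not tell the site whether the old PET may be reused: the MRI has an express 90-day allowance and the PET has none.

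Finally, the numbers affected are probably small at one site with 22 planned subjects. That limits the scale of the problem but does not remove the contradiction.

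**Conclusion.** The concern holds: the text is wrong as written on both counts and should be fixed. Exclusion 4 gives opposite answers for earlier exposure above 0 and up to 2.6 mSv. The reading that admits those subjects allows a combined exposure of up to 13.7 mSv once a third scan is taken. The re-screening instruction cannot be followed after a valid PET without breaking the third-scan rule.

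The conclusion rests on the wording of the sections and on the stated maximum of 3.7 mSv per scan. The 14.8 mSv case further needs two valid screening PETs, each followed by a non-imaging failure, with neither counted as earlier exposure. The documents give no frequency for that case, and it should be read as what the text permits, not as what is expected.

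**What to change.** Reconcile Table 2 footnotes a and m with Sections 7.3.2, 7.4, 8.2 (Exclusion 4), 10.3.1, 11.4 and 11.9.1 so that the eligibility threshold, the maximum number of scans and the stated total dose agree. Specifically:

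- State in Exclusion 4 which study dose enters the sum: the two-scan figure or the maximum.
- State how a screening PET already acquired is counted under Exclusion 4, and how it is handled at re-screening.

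Which limit or rule should prevail is for the sponsor and the responsible clinical and radiation-protection advisers; none is proposed here.

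The cost is a protocol clarification, with the approvals that Section 17.5 requires for any revision. The possible downside is slightly fewer re-screens or eligible subjects. No analysis has to change.

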## 9. STUDY DRUG MATERIALS AND MANAGEMENT

### 9.1. Description of Study Drug

**Table 5: Investigational Product**

| Attribute                              | Investigational Product   |   |
|--|---|---|
| Product name                           | SEP-363856  | SEP-363856  |
| Dosage form                            | Tablet  | Tablet  |
| Unit dose                              | 50 mg   | 75 mg   |
| Route of administration                | Oral  | Oral  |
| Physical description                   | Yellow oval tablet  | Yellow oval tablet  |
| Active Pharmaceutical ingredient (API) | SEP-363856-01(hydrochloride salt)   | SEP-363856-01 (hydrochloride salt)  |
| Excipients                             | 
 
-Microcrystalline cellulose
 
-Mannitol
 
-Sodium starch glycolate
 
-Magnesium stearate
 
Film coating:
 
-Hydroxypropyl methylcellulose
 
-Hydroxypropyl cellulose
 
-Titanium dioxide
 
-Yellow iron oxide
 
Carnauba wax
 
 | 
 
-Microcrystalline cellulose
 
-Mannitol
 
-Sodium starch glycolate
 
-Magnesium stearate
 
Film coating:
 
-Hydroxypropyl methylcellulose
 
-Hydroxypropyl cellulose
 
-Titanium dioxide
 
-Yellow iron oxide
 
Carnauba wax
 
 |

### 9.2. Study Drug Packaging and Labeling

#### 9.2.1. Package Description

Study drug will be provided in one-week blister cards containing 9 tablets (7 days + 2 extra days) SEP-363856 50 mg or 75 mg.

#### 9.2.2. Labeling Description

All packaging for the study drugs will be labeled with:

- Protocol number
- Sponsor's name and address
- Compound/Code or name of investigational drug and dosage form
- Contents (eg number of tablets)
- Investigational drug/Caution statement
- Instructions for use and storage
- Batch number
- Blank space for subject identifiers

- Period of use (as required)
- Unique medication/kit ID number
- Investigator information (if needed)

